#### **8.4.2 Multicenter Studies**

Patients will be enrolled at approximately 10 sites. To reduce variability, one rater should perform each clinician dependent assessments (SALT) for the patient for the duration of the study. All investigators using the SALT will be trained prior to use. Data from all sites will be pooled.

#### **8.4.3 Assessment Visit Windows**

The visit schedule for all study assessments is provided in Appendix [17.2](#). Patients will be considered completed for efficacy analyses after Week 24 (Visit 10). Patients will either complete treatment at Week 24 and have a Safety Follow-up visit at Week 28 prior to exiting the study, or if eligible, may enroll into an open-label extension study of CTP-543 at their Week 24 visit.

For scheduled visits, there will be no reassignment of the analysis visit based on date, and all data will appear in summary tables based on the nominal timepoint.

Both unscheduled visits and repeat visits will be reassigned to the closest prior visit. If an assessment was already documented at that visit, the scheduled data will be used in summaries. If the scheduled data was missing, then the re-assigned unscheduled visit/repeat visit will be used in summaries. All visits will be included in by-patient data listings.

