Less than $75 \times 10^9/L$	Interrupt dose until recovered to greater than $75 \times 10^9/L$ and resume dosing at previous dose
Greater than $750 \times 10^9/L$	Interrupt dose until recovered to less than $600 \times 10^9/L$ and resume dosing at previous dose

Upon dose interruption, the parameters that triggered the interruption should be monitored at least weekly until either: 1) recovery above the threshold for dosing resumption is achieved, or 2) the allowable 21-day interruption has elapsed. In the case of severe neutropenia (neutrophil counts less than $0.5 \times 10^9/L$) patients should discontinue the study drug and receive instructions to seek medical help if they develop fever or signs of infection. Patients who discontinue the study due to lack of acceptable recovery of parameters within 21 consecutive day dose interruption period should continue to be monitored as appropriate through acceptable clinical resolution.

If the patient recovers above the threshold for interruption before the 21 consecutive day interruption period ends, they may remain in the study. Subsequent dose interruptions within a patient should be discussed with the Medical Monitor to determine continued participation in the study.

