Clinical laboratory variables will be presented in 3 ways. First, change from Baseline to each scheduled assessment will be summarized descriptively. Baseline will be defined as the laboratory value obtained before the first dose of study drug on Day 1; if Day 1 values are unavailable, then values obtained at the Screening Visit will be used.

Second, treatment-emergent potentially clinically significant (PCS) laboratory values will be identified. Potentially clinically significant values are defined as those that meet Grade 3 or Grade 4 toxicity criteria from the CTCAE criteria. Treatment-emergent PCS laboratory values are those in which the baseline value is not PCS and the post-baseline value is PCS.

Third, treatment-emergent adverse events that result in dose interruption will also be identified.

The mean change from Baseline to each scheduled assessment will be summarized descriptively by dosing regimen for each clinical laboratory variable specified in this protocol.

The number and percentage of patients with Abnormal, clinically significant laboratory values (per Investigator judgment) and the number and percentage of patients with treatment-emergent PCS laboratory values will be summarized by dosing regimen for each clinical laboratory variable.

Vital Signs

The mean change from baseline to each scheduled assessment will be summarized descriptively by dosing regimen for each vital sign variable specified in this protocol.

Baseline will be defined as the last vital sign value obtained before the first dose of study drug on Day 1; if Day 1 values are unavailable, then values obtained at the Screening Visit will be used.

Electrocardiogram

The change from baseline in electrocardiogram intervals (PR, QT, QTcF, QRS, and RR) to each scheduled assessment will be summarized descriptively by dosing regimen.

Exploratory Endpoints

VAS scale for eyebrows will be tabulated and analyzed by dosing regimen, as appropriate.

Patient reported outcomes of satisfaction of hair coverage and satisfaction of hair coverage quality will be tabulated and analyzed by dosing regimen, as appropriate.

Additional detail will be outlined in the Statistical Analysis Plan.

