### **9.3 Clinical Laboratory Evaluation**

Observed measurements along with change from baseline for each assessment will be summarized descriptively by dosing regimen and visit for each clinical laboratory parameter.

Hematology parameters for patients that meet Grade 3 or Grade 4 toxicity criteria from the CTCAE v4.0 will be summarized for each scheduled visit and overall for all post-baseline visits. In addition, hematology parameters of interest will be plotted as mean values over time. Serum chemistry parameters for patients that meet Grade 3 or Grade 4 toxicity criteria from the CTCAE v4.0 will be summarized for each scheduled visit and overall for all post-baseline visits.

Laboratory values will be converted to International System of Units (SI) before analysis. If laboratory values are recorded as above or below a threshold (i.e. “<2”, “>30”, etc.), they will be counted as missing for continuous summaries. Abnormal, clinically significant laboratory values (per Investigator judgment) will be reported and summarized as AEs.

All laboratory parameter results will be included in by-patient data listings. Reference ranges for each clinical laboratory parameter will also be summarized in a data listing.

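### The SAP's visit rule keeps unscheduled laboratory draws out of the by-visit Grade 3-4 tables, leaves the overall row unclear, and omits the protocol's treatment-emergent condition without declaring it

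*SAP*

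**What the plan says.** SAP 8.4.3 states the visit rule: "Both unscheduled visits and repeat visits will be reassigned to the closest prior visit". It continues: "If an assessment was already documented at that visit, the scheduled data will be used in summaries". The reassigned value enters a summary only if the scheduled one is missing. The section sits under the efficacy chapter but opens on a wider scope ("The visit schedule for all study assessments is provided in Appendix" 17.2), and SAP Section 9 contains no separate rule for unscheduled or repeat laboratory draws. Unused values are kept: "All visits will be included in by-patient data listings".

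SAP 9.3 says that hematology and chemistry results meeting CTCAE Grade 3 or 4 "will be summarized for each scheduled visit and overall for all post-baseline visits". It sets no condition on the baseline value.

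The protocol relies on draws outside the schedule. Section 8.2 asks for repeat testing before an interruption, at the next protocol visit or an unscheduled one, except in severe cases. During an interruption, "the parameters that triggered the interruption should be monitored at least weekly", for up to 21 days. Section 9.10 names confirmation of hematology results for interruption or resumption as a purpose of an unscheduled visit. Section 9.9 asks that clinically significant results be repeated.

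Protocol 11.4.4 defines potentially clinically significant (PCS) values as CTCAE Grade 3 or 4 and adds: "Treatment-emergent PCS laboratory values are those in which the baseline value is not PCS and the post-baseline value is PCS". It promises the number and percentage of such patients by regimen. SAP Section 12 lists one change from the protocol, the added absolute SALT thresholds.

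**The concern.** The visit rule does little harm to SALT, which has no planned off-schedule assessments. It falls mainly on safety laboratory data, where extra draws are taken because something is wrong. A draw taken to follow a falling count is matched to an earlier visit that normally already has a result, and it loses to that result.

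Tolerability is part of the study's overall objective, cytopenia is a named managed risk, and all safety summaries are descriptive. The Grade 3-4 tables are therefore a main part of the tolerability comparison. If the rule is applied literally they can understate the worst values. If one programmer includes unscheduled draws in the overall row and another does not, the same data give two different counts.

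The baseline condition is a second, separate problem. Without it, a patient who was already Grade 3-4 before dosing and stays there is counted in the same way as one who became Grade 3-4 on treatment.

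**Working it through.** The documents give no figure for this point, so there is nothing to reproduce. The check is textual, with simple arithmetic.

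**Where the draws go.** Protocol Table 1 schedules on-treatment laboratory tests at Weeks 2, 4, 6, 8, 12, 16, 20 and 24. The gaps from Day 1 are 14, 14, 14, 14, 28, 28, 28 and 28 days.

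- After Week 8: 28 − 21 = 7, so an interruption of the full 21 days fits between two scheduled draws with 7 days to spare. Monitoring at least weekly gives at least 21 / 7 = 3 draws. All map to the preceding visit and are set aside if that visit has a value.
- Up to Week 8: 21 > 14, so a full-length interruption spans at least one scheduled draw, which is summarized. Only the draws between visits are lost.
- Between Day 1 and Week 2: an unscheduled draw maps to Day 1, which is the baseline visit, although it was taken on treatment.

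**Illustration with invented values** (neutrophils, × 10⁹/L): Week 8 scheduled 1.6; unscheduled 0.9, 0.4 and 0.8; next scheduled draw 1.7.

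- Minimum in the by-visit tables: min(1.6, 1.7) = 1.6.
- True minimum: 0.4, below the 0.5 that Protocol 8.2 calls severe neutropenia.

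At that level Protocol 8.2 has the patient stop study drug, so the next scheduled draw could be the early termination visit instead of Week 12. The by-visit minimum is 1.6 either way. The documents do not reproduce the CTCAE cut-offs, so the protocol's own threshold serves as the marker.

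If the trigger was itself a scheduled value, say 0.9 followed by an unscheduled 0.4, the low trigger stays in the table. What is lost is the depth of the fall, and not necessarily the patient.

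**Size of one miss.** With about 30 patients per arm, 1 / 30 = 3.3 percentage points.

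**How likely a miss is.** This needs two quantities that the documents do not give: p, the share of patients with an on-treatment Grade 3-4 value, and f, the share of those whose Grade 3-4 value is seen only at unscheduled draws. For 60 patients,

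P(at least one missed) = 1 − (1 − p·f)^60.

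| Assumed p | f = 10% | f = 25% | f = 50% |
|---|---|---|---|
| 2% | 11% | 26% | 45% |
| 5% | 26% | 53% | 78% |
| 10% | 45% | 78% | 95% |

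A rough anchor for p: Protocol 4.4.1 reports 3 Grade 3 or 4 hematologic changes in the interim data of the earlier Phase 2 study, spread equally over the 4 mg, 8 mg and placebo groups, so 1 per group. Group sizes are not stated. If the approximately 125 patients were split equally over four groups, that is 1 / (125 / 4) = 3.2%, or 30 × 0.032 ≈ 1 patient per arm here. With p = 3.2% the formula gives 17%, 38% and 62% for the three values of f. This anchor covers hematology only.

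**Treatment-emergent condition.** Protocol 11.4.4 counts a patient when baseline is not Grade 3-4 and a post-baseline value is. SAP 9.3 counts a patient when a value is Grade 3-4. The second set contains the first, plus patients who were already Grade 3-4 at baseline. The omission can only raise the count. SAP Section 1 says changes from protocol-specified analyses will be documented in the SAP; Section 12 does not list this one.

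**The case against.** The strongest reply is that most of these events are tabulated elsewhere. Protocol 10.1 makes a laboratory abnormality an adverse event if it leads to study discontinuation, or if the investigator judges it important enough to need interruption or treatment. Adverse events are graded by CTCAE, and each patient is counted at the highest severity. SAP Tables 14.3.1.5 to 14.3.1.7 cover events causing interruption and Grade 3-4 hematology and chemistry events, and none depends on a scheduled visit. A patient like the one in the illustration would normally appear there. This stands, and it limits the harm. It does not remove the point: those tables rest largely on investigator judgment, whereas Protocol 11.4.4 promises a grade-based count in addition to the judgment-based one. Listings do not give rates by regimen.

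Three stronger readings are tempting, and the documents do not support them.

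- A reader might infer that unscheduled values are also excluded from the overall Grade 3-4 row. SAP 9.3 contrasts each scheduled visit with all post-baseline visits, and the second phrase can include unscheduled draws. This is an ambiguity, which the separate table shells, not available here, may settle.
- A reader might infer that omitting the treatment-emergent condition also hides bad values. It works the other way.
- A reader might infer that results reported as < or > are deleted. SAP 9.3 says "they will be counted as missing for continuous summaries", so they stay in the listings and nothing takes them out of Grade 3-4 counts. That rule is not part of this point.

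It is also fair to say that the baseline condition matters least for cytopenia, because neutrophils, platelets and hemoglobin have explicit entry limits. Chemistry parameters such as creatine kinase, lipase and amylase have no named limit, but exclusion 13 is open-ended, so few such patients may enter.

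**Conclusion.** The point holds in two parts. First, as written, SAP 8.4.3 removes unscheduled and repeat laboratory values from the by-visit laboratory and Grade 3-4 summaries whenever a scheduled value exists, and SAP 9.3 does not say whether the overall row restores them. This assumes that 8.4.3 governs laboratory data, which its opening sentence and the absence of any rule in Section 9 support. Second, the protocol's treatment-emergent count is missing from the SAP and the change is undeclared. The two errors run in opposite directions and should not be expected to cancel.

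Each missed patient shifts an arm's rate by 3.3 percentage points, and the expected count may be only about one per arm. The probability of a miss ranges from 11% to 95% under assumed inputs, so it shows sensitivity and is not an estimate. The plan should be corrected before database lock. The SALT analyses are not affected by this point, and safety signals are not lost altogether, because the adverse event tables and listings remain.

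**What to change.** In SAP 9.3, state that the overall post-baseline Grade 3-4 tables for hematology and chemistry use each patient's worst post-baseline value from any scheduled, repeat or unscheduled draw. Define post-baseline by the time of the draw relative to first dose and not by the assigned visit, so that draws before Week 2 are not absorbed into Day 1. In SAP 8.4.3, limit the scheduled-value rule to by-visit descriptive summaries.

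For treatment-emergent counts, restore the Protocol 11.4.4 condition that baseline was not Grade 3-4.

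The cost is SAP wording, a little more derivation and possibly a table shell edit. No new data are needed. Reported Grade 3-4 counts may change in either direction: up from the added draws, down from the baseline condition.

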### **8.5 Analysis Methods**

No formal hypothesis tests will be conducted. All confidence intervals will be 90%. Testing will be based on the Efficacy Population and performed only for the Treatment Period.

[Table 8-1](#) gives an overview of the analysis methods that will be used for each of the efficacy variables.

**Table 8-1 Efficacy Variables and Analysis Methods**

Efficacy Variables	Collection Times	Method
Primary		
SALT (relative change)	Baseline, Week 24	Mean and 90% confidence interval (t-distribution)
Secondary		
Responder Analysis	Baseline, Week 4, 8,	Proportion and 90%
SALT (90%, 75%, 50% relative reduction)	12, 16, 20, 24	confidence interval (binomial approximation)
SALT (absolute change)	Baseline, Week 4, 8, 12, 16, 20, 24	Mean and 90% confidence interval (t-distribution)
SALT (relative change)	Baseline, Week 4, 8, 12, 16, 20, 24	Mean and 90% confidence interval (t-distribution)
Satisfaction of hair coverage	Baseline, Week 24	Proportion and 90% confidence interval (binomial approximation); Shift table
Exploratory		
VAS for Eyebrows (percent change)	Baseline, Week 24	Mean and 90% confidence interval (t-distribution)
Satisfaction of hair coverage quality	Baseline, Week 24	Proportion and 90% confidence interval (binomial approximation); Shift table
SALT ( $\leq 10$ , $\leq 20$ , $\leq 25$ absolute score)	Baseline, Week 4, 8, 12, 16, 20, 24	Proportion and 90% confidence interval (binomial approximation)

### 8.5.1 Primary Efficacy Analysis

The aim of this study is to compare 16 mg doses of CTP-543 taken in 2 different dosing regimens (8 mg BID or 16 mg QD). Comparisons between dosing regimens will be assessed using the mean relative change from baseline at Week 24 with 90% confidence intervals.

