6.4 Method of Treatment Assignment

Patients meeting screening criteria will continue to the Day 1 Randomization Visit for review of eligibility and baseline assessments, including SALT assessment, physical examination, clinical laboratory assessments, vital signs, and electrocardiogram. Patients meeting all eligibility criteria will be randomized to 1 of 2 CTP-543 treatment arms (8 mg BID or 16 mg QD).

Randomization will also be stratified by classification of alopecia areata subtype into one of the following three categories: 1) alopecia areata, 2) alopecia totalis or alopecia universalis, or 3) alopecia ophiasis.

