11.4.2. Efficacy

For the primary efficacy endpoint and other continuous measures, a 90% confidence interval for the dosing regimen difference at Week 24 will be calculated using the t-distribution. For categorical measures (e.g. proportion of responders), a 90% confidence interval for the dosing regimen difference at Week 24 will be calculated based on normal approximation for the binomial distribution, using the Wald continuity correction $[(1/n_1 + 1/n_2)/2]$.

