### **2.2 Study Design**

This is a randomized, parallel group multicenter study to evaluate the efficacy and tolerability of two dosing regimens of CTP-543 (8 mg twice daily dosing (BID) vs 16 mg once daily dosing (QD)), in adult patients with chronic, moderate to severe alopecia areata. Patients will be between 18 and 65 years of age and experiencing an episode of alopecia areata lasting at least 6 months and not exceeding 10 years, with at least 50% hair loss as measured by the Severity of Alopecia Tool (SALT) at Screening and Baseline, and are not concurrently being treated for alopecia areata with other treatments that might affect hair regrowth or immune response. Up to approximately 75% of alopecia areata patients with alopecia totalis or universalis, and no more than 10% with only alopecia ophiasis will be enrolled.

Patients may be screened up to 28-days prior to initiation of study drug. The Treatment Period is a 24-week dosing period where patients will be randomized to receive either CTP-543 8 mg BID, or CTP-543 16 mg QD and will be analyzed for the primary endpoints of the study. To minimize bias in the evaluation of study endpoints, patients, investigators, and site personnel will be unaware of the active drug dosing regimen by administering one 16 mg tablet and one placebo tablet 12 hours apart from each other for the 16 mg QD study group.

Patients will take the first dose of study drug in the clinic on Day 1. Patients will be instructed to take study drug every 12 hours. Patients should dose study drug in the clinic on all Study Visit Days after clinical laboratory blood draws are completed.

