Patient safety will be monitored throughout the trial. The patient will be tested to ensure they do not have the Hepatitis B or C virus, thyroid function abnormalities or latent or active Tuberculosis, during the screening period. During the first 8 weeks of the Treatment Period, hematology and serum chemistry will be conducted every 2 weeks, followed by an assessment every 4 weeks thereafter through completion of the study at 24 weeks. Lipid levels will be assessed every 12 weeks throughout the Treatment Period. Significant cytopenias or other hematologic abnormalities will be managed by severity through dose interruption, or discontinuation, and signs and symptoms of infection will be closely monitored and treated promptly. Patients who experience intolerable symptoms during treatment may discontinue the study at the discretion of the Investigator. Patients may withdraw consent at any time. The Treatment Period will last 24 weeks to assess BID and QD doses, in parallel. Assessment of treatment response with SALT for efficacy will occur at 4, 8, 12, 16, 20 and 24 weeks. Upon completion of the 24-week Treatment Period patients will be eligible to either complete

treatment and exit the study following the safety follow-up visit, or roll-over into a long-term open-label extension study.

Approximately 60 patients are planned to be enrolled in the study; approximately 30 patients per dosing regimen.

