### **2.5 Treatment Group Assignments or Randomization**

Patients meeting all inclusion criteria and none of the exclusion criteria will be randomized to CTP-543 8 mg BID or CTP-543 16 mg QD in a 1:1 ratio. Randomization will be stratified by classification of alopecia areata subtype into one of the following three categories: 1) alopecia areata, 2) alopecia totalis or alopecia universalis, or 3) alopecia ophiasis.

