### **2.6 Sample Size Determination**

A sample size of 25 patients (completers) per group provides adequate precision for the estimated dosing regimen difference for relative change in SALT score from baseline at Week 24. Precision of the estimated difference is quantified by the width of the 90% confidence interval (CI) for the dosing regimen difference.

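### The primary comparison ignores the stratification factor (alopecia subtype) and baseline SALT, and SAP 8.5.1 and Table 8-1 do not say that the 90% interval is for the regimen difference

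*SAP*

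**What the plan says.** Protocol 6.4 states: "Randomization will also be stratified by classification of alopecia areata subtype". SAP 2.5 repeats this with three categories: patchy alopecia areata, totalis or universalis, and ophiasis. Ophiasis is capped in SAP 2.2 ("no more than 10% with only alopecia ophiasis will be enrolled"), and the same section gives the planned size: "Approximately 60 patients are planned to be enrolled in the study".

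For the primary endpoint, relative change in SALT at Week 24, protocol 11.4.2 plans this analysis: "a 90% confidence interval for the dosing regimen difference at Week 24 will be calculated using the t-distribution". SAP 2.6 relies on the same quantity: "Precision of the estimated difference is quantified by the width of the 90% confidence interval (CI) for the dosing regimen difference".

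Where the SAP specifies the primary analysis, the wording is looser. Section 8.5.1 reads: "Comparisons between dosing regimens will be assessed using the mean relative change from baseline at Week 24 with 90% confidence intervals". The Table 8-1 entry for the primary variable is "Mean and 90% confidence interval (t-distribution"). Neither mentions a difference, a stratum, a covariate or a model.

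Subtype reappears only in the by-subtype summaries of SAP 8.5.2 (descriptive statistics with 90% intervals) and SAP 8.6. Baseline SALT appears only as the denominator of relative change (SAP 8.1.1). SAP 12 lists no change to the primary analysis.

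**The concern.** There are two linked points.

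**No adjustment.** If subtype predicts response, stratified randomisation balances it between arms, so the true sampling variance of the difference falls. The pooled SD in an unadjusted t-interval still contains the between-subtype variance. The interval is then too wide and covers more than its stated 90%. The estimate itself is not biased.

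**The target of the interval is not named.** Table 8-1 uses the same method entry for the eyebrow VAS, and SAP 8.5.3 describes that interval as being around the mean. SAP 8.5.2 asks for intervals for each regimen in the line graphs. A programmer working from 8.5.1 and Table 8-1 alone could produce one interval per arm and none for the difference.

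The study has no hypothesis test, and its stated aim is to compare two regimens. The interval for the difference is therefore its main inferential result. With 25 to 30 patients per arm that interval is already wide.

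**Working it through.** **Inputs from the documents.** 25 completers per group (SAP 2.6); about 30 enrolled per regimen (SAP 2.2); 1:1 allocation (SAP 2.5); 90% intervals and no tests (SAP 8.5); ophiasis at most 10%. The Efficacy Population needs only one post-treatment SALT score and LOCF is used (SAP 4.1, 8.4.1), so the analysed number should lie nearer 30 than 25.

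**Assumptions.** The documents give no SD, no target width and no R² for subtype. The choice of 25 per group therefore cannot be reproduced. SD is taken as 30, 40 or 50 percentage points, and subtype R² as 0, 0.05, 0.10 or 0.20.

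**Step 1. Unadjusted interval for the difference.** Half-width = t(0.95, 2n-2) × SD × √(2/n).
- n = 25: 1.677 × √(2/25) = 0.474 SD, or 14.2, 19.0 and 23.7 points.
- n = 30: 1.672 × √(2/30) = 0.432 SD, or 12.9, 17.3 and 21.6 points.

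**Step 2. If only per-regimen intervals were reported.** The two intervals together bound the difference with half-width 2 × t(0.95, n-1) × SD/√n.
- n = 25: 2 × 1.711/√25 = 0.684 SD.
- n = 30: 2 × 1.699/√30 = 0.620 SD.

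That is about 1.44 times the half-width in Step 1. Simulated coverage for the difference (400,000 runs, normal data with equal variances) is 98.0%.

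**Step 3. Effect of ignoring subtype.** With arms balanced within strata, the unadjusted interval covers 2F(t/√(1-R²)) - 1, where F is the t distribution function on 2n-2 df. Adjusting for two-level subtype alone multiplies the width by [t(0.95, 2n-3)/t(0.95, 2n-2)] × √(1-R²). At n = 25:

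| Subtype R² | Coverage of unadjusted 90% interval | Width ratio, subtype only |
|---|---|---|
| 0 | 90.0% | 1.000 |
| 0.05 | 90.8% | 0.975 |
| 0.10 | 91.7% | 0.949 |
| 0.20 | 93.3% | 0.895 |

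Simulating trials with a totalis/universalis share of 50% or 75% gave width ratios of 1.001, 0.975, 0.948 and 0.893. A separate simulation (40,000 trials, three-level subtype split 12/11/2 in each arm) gave unadjusted coverage of 90.1, 91.7 and 93.6% at R² of 0, 0.10 and 0.20.

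**Step 4. The full proposed model.** This has two-level subtype plus baseline SALT. Baseline is set to 100 for totalis/universalis and uniform on 50 to 100 otherwise, with no effect of its own. These are assumptions, and they make baseline a pure cost.

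| Subtype R² | Width ratio, n = 25 | Width ratio, n = 30 |
|---|---|---|
| 0 | 1.012–1.013 | 1.010 |
| 0.05 | 0.986–0.987 | 0.983–0.985 |
| 0.10 | 0.959–0.960 | 0.956–0.958 |
| 0.20 | 0.903–0.905 | 0.901–0.903 |

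Coverage of the adjusted interval is 89.9 to 90.0%. Break-even R² is 1 - 1/1.012² = 0.024 at n = 25 and 1 - 1/1.010² = 0.020 at n = 30.

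**Step 5. The ophiasis stratum.** 10% of 60 is 6 patients, about 3 per arm, which is too few to carry a level of its own.

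**The case against.** **The unadjusted interval is valid.** It is the protocol's own method, it is unbiased under 1:1 stratified randomisation, and no margin, target width or decision rule depends on how wide it is. All of that stands. The loss is of precision only, which is why this is a recommended change and not a required one.

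**The gain rests on an R² that the documents do not give.** This also stands. For a two-level factor, the gap between subtype means needed for a given R² is √(R²/(p(1-p))) × SD. At SD 40 and a totalis/universalis share p of 50 to 75%, the n = 25 break-even of 0.024 needs a gap of about 12 to 14 points, R² 0.10 needs about 25 to 29, and R² 0.20 needs about 36 to 41. No response by subtype is reported to support any of these. On a half-width of 19.0 points, the net change runs from about +0.2 to -1.8 points. Stratifying on subtype and capping enrolment by it suggest that the sponsor thinks it matters, but they do not say how much.

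**Baseline SALT may add little.** Totalis/universalis patients have complete scalp hair loss by definition, and relative change already divides by baseline. This is fair, and no gain from baseline beyond subtype is claimed here.

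**By-subtype intervals are already planned in SAP 8.5.2.** They are, but they do not adjust the primary comparison.

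**The difference is named elsewhere.** Protocol 11.4.2, the protocol synopsis and SAP 2.6 all name it. SAP 8.5.1 speaks of comparisons, SAP 12 records no change, and the table shells are not available to read. The mean, SD and n required by SAP 3 would also let a reader compute the unadjusted interval. So this half is a gap in wording at the two places that specify the primary analysis, and no departure from the protocol is shown.

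**Conclusion.** The concern holds as a recommended change, with medium confidence. The primary comparison uses neither the randomisation stratum nor baseline SALT as a covariate, and SAP 8.5.1 and Table 8-1 do not name the quantity that the interval estimates.

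The cost of leaving it is modest and depends on an unknown. It is nil if subtype is not prognostic. At a subtype R² of 0.20, the unadjusted interval is about 10% wider than it need be and over-covers by about 3 percentage points. The calculations assume normal outcomes with equal variance, arms balanced within strata, and no added value from baseline SALT. The 1.44-fold loss in Step 2 arises only if the ambiguous wording leads to per-regimen intervals being reported alone.

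**What to change.** In SAP 8.5.1 and Table 8-1, state that the QD minus BID difference in mean Week 24 relative SALT change, with its 90% CI, is estimated from a linear model with regimen, subtype (totalis/universalis versus all other) and baseline SALT. Fix in advance that ophiasis is pooled with patchy disease, because about 6 patients cannot support a separate level. Keep the unadjusted t-interval of protocol 11.4.2 as a sensitivity analysis, and record the adjustment in SAP 12 before database lock.

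If adjustment is declined, 8.5.1 and Table 8-1 should still name the unadjusted 90% CI for the regimen difference.

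No new data are needed. The model spends two degrees of freedom and widens the interval by about 1.0 to 1.3% if neither covariate is prognostic. Naming the difference is a change of wording only.
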